## 13.2 PROCEDURES FOR ADVERSE EVENT RECORDING

An AE report will be created for each observed event and keep with the study records. Both co-PIs will review and sign all generated AE reports. At the time the AE is reported the causality relationship to the study procedures will be determined by the co-PIs. The AE reports will be reviewed by an external, unbiased expert at defined intervals as described in Section 12.1.

Additionally, all observed SAEs will prompt the creation of a report which will be handled in a similar manner to that described for any observed AE. All SAE reports will be completed within 24-48 hours of learning of their occurrence. The SAE reports will also be shared with the IRB once they are completed.

## 14 PROTOCOL DEVIATIONS

This trial will be conducted as described in this protocol, except for an emergency situation in which the protection, safety, and well being of the subject requires immediate intervention, based on the judgment of the investigator. In the event of a significant deviation from the protocol due to an emergency, accident, or mistake, the investigator or designee will report the deviation to the UHCMC IRB in a timely manner (i.e. within approximately one business week from learning of the deviation). The UHCMC IRB will be informed of all protocol changes by the principle investigator in accordance with established procedure. No deviations of any type will be made without complying with all the UHCMC IRB established procedures.

## **15 STATISTICAL PLAN**

All collected data in the case report form will be transferred into a customized electronic database upon completion of the study for the purpose of facilitating statistical analysis.

Preoperative demographics and clinical variables will be compared in the two groups to assess for significant differences using the independent t-test. Differences in the observed clinical data between groups will be determined with the Wilcoxon rank-sum test. Stepwise, forward, multivariable logistic regression analysis will be performed to assess for relationships between cerebral desaturations and any of the measured clinical variables with a p value < 0.05 being considered significant.

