#### **6.4 Exploratory Objectives**

Exploratory objectives will include performing all possible comparisons of the two groups based upon all collected perioperative variables to examine the potentially significant relationships between the collected clinical variables representing surrogates of organ perfusion/function and cerebral oximetry desaturations (AUCrSO2). The following exploratory endpoints will be assessed:

- Logistic regression analysis to determine the most relevant AUCrSO2 desaturation value(s) associated with any detrimental clinical outcome(s) monitored in this study
- Logistic regression analysis to determine the most relevant AUC blood pressure values associated with any detrimental clinical outcome(s) monitored in this study
- Comparison of baseline rSO2 values (room air and oxygen supplemented) to all collected clinical variables to assess for possibly significant associations

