### **7 STUDY DESIGN**

#### **7.1 Study Design**

This study is a single center (University Hospitals Case Medical Center), prospective, randomized, controlled pilot study of elderly thoracic surgical patients undergoing procedures involving the use of SLV. A total of 100 eligible subjects will be randomized in a balanced fashion (1:1) to either the control cohort that will have electronically blinded bi-frontal cerebral oximetry monitoring or the intervention cohort that will have open bi-frontal cerebral oximetry monitoring with a predefined intervention protocol for observed desaturations of greater than 20% of established oxygen supplemented baseline values (see Appendix C). Both the control and intervention groups will have baseline NIRS data obtained in an unblinded fashion. The study will be divided into four separate periods that include screening, baseline acquisition, intraoperative and immediate postoperative and the postoperative follow up period.

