## **Schematic Diagram of Trial Design**

## 7.4 Study Variables

### 7.4.1 Primary Endpoints

The relationship between the observed cerebral oximetry data and a number of predefined intraoperative and postoperative clinical variables will serve as the primary endpoints of this trial. The clinical variables will include the following intraoperative and postoperative (PACU or initial 12 hours of the ICU stay) parameters:

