$AUC_{SpO_2} < 75\%$  regardless of intraoperative  $FiO_2$  values

$AUC_{SpO_2} < 70\%$  regardless of intraoperative  $FiO_2$  values

- Time from procedure completion to arrival in the post anesthesia care unit (PACU) or ICU
- Temperature upon PACU/ICU arrival
- Aldrete score upon PACU/ICU arrival and at 30 & 60 (or at discharge) min post-PACU arrival (See Appendix A)
- Any occurrence of immediate postoperative atrial fibrillation
- Any myocardial ischemia in the immediate postoperative period
- Any need for allogeneic RBC transfusion in the immediate postoperative period
- Any observed stroke or TIA in the immediate postoperative period
- Time to clinical readiness for PACU discharge as assessed by established institutional discharge criteria (see Appendix B)
- Frequency and severity of nausea and vomiting observed in the PACU and/or ICU as assessed by an accepted postoperative nausea and vomiting scale
- ICU length of stay (ICU-LOS) [anticipated to be at least 10-20 evaluable subjects for this parameter if 100 patients are enrolled] which will be defined as time to clinical readiness for ICU discharge as assessed by the clinical team caring for the patient
- Postoperative mechanical ventilation time if still intubated and admitted to the ICU following the surgical procedure
- Use of any immediate postoperative, intravenous vasopressor and/or inotropic agent (as assessed by amount of time in minutes on any IV drug support regardless of dose and assessed by total dose of drug delivered to patient)
- Immediate postoperative urine output in any patient with an indwelling foley catheter as assessed by mLs urine/kg/hr for total time in operating room
- Hospital length of stay (H-LOS)
- Need for skilled nursing facility/rehabilitation hospital admission upon discharge from index hospitalization
- Length of time spent in a skilled nursing facility/rehabilitation hospital upon discharge from index hospitalization if a relevant data point for each subject

- Need for hospital readmission for any reason within 30 days of surgical procedure
  - Observed change from preoperative baseline Mini-mental Status Examination (MMSE) score (including postoperative day #1 and postoperative day #3 or discharge scores)
  - Presence/absence of postoperative delirium (as assessed by the CAM Delirium assessment tool results obtained preoperatively and postoperatively upon PACU discharge, Day#1 and 3 [or hospital discharge])

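### Section 15 names only logistic regression, with no dependent variable, for relating desaturation to clinical variables; for non-binary outcomes this implies a cut costing about 36% of the information at a median split and 51% at 80/20 (normality assumed)

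*Combined protocol and SAP*

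**What the plan says.** Section 15, repeated in the synopsis under Statistical Methods, names three methods. Preoperative variables are compared by t-test. For the randomised arms, "Differences in the observed clinical data between groups will be determined with the Wilcoxon rank-sum test". For association, "Stepwise, forward, multivariable logistic regression analysis will be performed to assess for relationships between cerebral desaturations and any of the measured clinical variables". The threshold for that model is given as follows: "with a p value < 0.05 being considered significant". No linear, rank, ordinal or time-to-event model is named for the association question, and no dependent variable is stated.

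Section 6.4 again names logistic regression, to find the rSO2 AUC "desaturation value(s) associated with any detrimental clinical outcome(s) monitored in this study", and likewise for blood-pressure AUC. That wording suggests the clinical outcome is the response and the AUC the predictor.

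The status of these analyses varies. Section 7.4.1 states: "The relationship between the observed cerebral oximetry data and a number of predefined intraoperative and postoperative clinical variables will serve as the primary endpoints of" the trial. Section 6.4 and the synopsis list the AUC regressions as exploratory.

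Section 7.4.1.2 lists many outcomes that are not yes/no, for example "Observed change from preoperative baseline Mini-mental Status Examination (MMSE) score", hospital stay, time to PACU readiness, GFR and creatinine change, Aldrete score and time to first bowel movement. On sample size, section 7.1 says: "A total of 100 eligible subjects will be randomized in a balanced fashion (1:1").

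**The concern.** Ordinary logistic regression takes a two-category response. A continuous, ordinal or time outcome can be its response only after being cut in two. If desaturation is made the response instead, the desaturation measure has to be cut. Either way, graded information from a small sample is reduced to above or below a line.

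At stake is what the pilot can learn. Its purpose is to choose endpoints for a larger trial (section 6.2), and the rationale in section 5 promises to quantify the relative strength of correlations between physiological measures and outcomes. For a continuous outcome, no named method does that without a cut. Real associations may be missed. For outcomes with no stated cut point, the position of the cut is also an open choice, made alongside forward selection at 0.05.

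**Working it through.** The plan gives no power, effect size or standard deviation, so there is no stated figure to reproduce. The check asks what a cut would cost.

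**Inputs from the documents.** n = 100 (section 7.1); alpha 0.05 (section 15; sidedness is not stated).

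**Assumptions not in the documents.** Two-sided test, bivariate normal data, linear association, the cut positions, and a true correlation of 0.28. The correlation was chosen because it is about the size detectable with 80% power at n = 100: tanh[(1.960 + 0.842)/√97] = tanh(0.284) = 0.277.

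**Step 1: information kept after a cut.** For a normal variable cut so that a share p lies on one side, large-sample efficiency relative to the uncut variable is φ(z_p)² / [p(1 − p)].

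- 50/50: 0.3989² / 0.25 = 0.637, a 36% loss; 100 subjects act like 64.
- 80/20: 0.2800² / 0.16 = 0.490, a 51% loss; 100 act like 49.
- 90/10: 0.1755² / 0.09 = 0.342, a 66% loss; 100 act like 34.

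The loss reaches one half at a split of about 79/21. Measured against a Spearman rank analysis (efficiency 9/π² = 0.912), it is 30% at 50/50 and 46% at 80/20.

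**Step 2: power by simulation.** n = 100, 5,000 runs per setting, one predictor and one outcome.

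| Analysis | Power at correlation 0.28 |
|---|---|
| Linear, outcome uncut | 81.1% |
| Spearman, outcome uncut | 77.3% |
| Logistic, outcome cut 50/50 | 63.6% |
| Logistic, outcome cut 70/30 | 58.8% |
| Logistic, outcome cut 80/20 | 52.4% |
| Logistic, outcome cut 90/10 | 38.7% |
| Logistic, desaturation cut 50/50, clinical variable uncut | 63.3% |
| Logistic, desaturation cut 80/20, clinical variable uncut | 52.0% |

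With no true association, every method rejected in 5.1% to 5.5% of runs, so the differences in power are not differences in test size. Against the linear analysis, a median cut costs 81.1 − 63.6 = 17.5 points and an 80/20 cut 81.1 − 52.4 = 28.7 points.

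**Step 3: which cut points the plan states.** For desaturation there are many. Section 6.3 gives 5% to 50% falls in 5% steps. Sections 7.4.1.1 and 7.4.1.2 give eight relative thresholds on each of two baselines and nine absolute ones. Among clinical outcomes, the composite in 7.4.1.2 fixes hospital stay at 4.5 days, PACU stay at 2 hours, a creatinine rise above 0.5 mg/dL and PONV at grade 2. None is stated for MMSE change, GFR change or time to bowel function.

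**The case against.** The strongest reply is that nothing in the plan says outcomes will be cut. Section 15 leaves the dependent variable open, and section 6.3 supplies a natural binary one: whether a patient had any desaturation of a given depth. Hospital stay or MMSE change could then enter uncut as candidate predictors. It also does not say that the logistic model is binary, and proportional-odds regression is a logistic model.

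Part of this stands. A reader might infer that the plan forces every continuous outcome into two categories; the documents do not support that, because dichotomisation is implied by the model and never stated. But the alternative moves the cut to desaturation, and the last two rows of the table show about the same loss. It also fits section 6.4 poorly, where the AUC is the predictor and one of the analyses concerns blood pressure, not desaturation. A proportional-odds model would meet much of the concern, but the plan does not name one.

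A reader might also infer that the whole trial loses a third to a half of its information. It does not. Section 6.2 and the synopsis criteria for evaluation put the primary question between the randomised arms, where the Wilcoxon test needs no cut and has efficiency 3/π = 0.955 against the t-test for normal data. Death, stroke, delirium, atrial fibrillation and readmission are already binary and lose nothing.

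Nor do the documents say that the missing cut points will be chosen after the data are seen. They leave the choice open, and for desaturation they list thresholds in advance, although none is designated for the model.

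Finally, the figures rest on assumptions. Skewed outcomes such as hospital stay will behave differently, the simulation is bivariate while the plan is stepwise and multivariable, and not every outcome has 100 subjects: ICU stay expects at least 10 to 20, ventilation time applies only to those still intubated, and urine output needs a catheter.

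**Conclusion.** The point holds for the association analyses of non-binary outcomes, which section 7.4.1 calls primary endpoints and section 6.4 calls exploratory. There, the only named model implies cutting the outcome or the desaturation measure. Under normality the cost is about 36% of the information at a median split, 51% at 80/20 and 66% at 90/10. At n = 100 and an assumed correlation of 0.28, simple bivariate power falls from about 81% (77% by ranks) to 64% or 52% at the first two cuts. These figures show the order of the loss; they are not the power of the planned stepwise analysis, and outcomes with few evaluable subjects start from much less. The change is worth making because a better-matched method needs no new data.

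**What to change.** In sections 6.4 and 15, and in the synopsis:

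- State that the clinical outcome is the dependent variable, with rSO2 AUC and blood-pressure AUC as continuous predictors.
- Keep binary logistic regression for yes/no outcomes.
- Use linear regression (on ranks or logs if skewed) or proportional-odds regression for continuous and ordinal outcomes such as MMSE change, GFR and creatinine change, and Aldrete score.
- Use Cox or proportional-odds regression for times such as hospital stay, PACU readiness and return of bowel function.
- Report any dichotomised version as descriptive only, with its cut point written down before analysis.

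The cost is SAP wording and standard software. The drawback is that results become slopes, common odds ratios or hazard ratios according to the outcome, instead of one odds ratio throughout, so outcomes are harder to compare side by side.

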#### 7.4.1.1 Intraoperative:

- Area under the curve of cumulative rSO2 desaturations (AUCrSO2) of progressive categorical degrees that will include the following:
  - < 5% of established room air baseline and oxygen supplemented baseline ○ < 10% of established room air baseline and oxygen supplemented baseline ○ < 15% of established room air baseline and oxygen supplemented baseline ○ < 20% of established room air baseline and oxygen supplemented baseline ○ < 25% of established room air baseline and oxygen supplemented baseline ○ < 30% of established room air baseline and oxygen supplemented baseline ○ < 35% of established room air baseline and oxygen supplemented baseline ○ < 40% of established room air baseline and oxygen supplemented baseline ○ < 60% of absolute measured value (if baseline > 60%) ○ < 55% of absolute measured value (if baseline > 55%) ○ < 50% of absolute measured value (if baseline > 50%) ○ < 45% of absolute measured value (if baseline > 45%) ○ < 40% of absolute measured value ○ < 35% of absolute measured value

○ < 30% of absolute measured value ○ < 25% of absolute

measured value ○ < 20% of absolute measured value

- Area under the curve for cumulative, high and low intraoperative values outside of preestablished, individualized patient blood pressure goals based upon preoperatively observed blood pressure values as well as values clinically accepted to provide adequate organ perfusion. This analysis will be performed for systolic, diastolic and mean arterial pressures (AUCSBP-hi, AUCSBP-low, AUCSBP-cum, AUCDBP-hi, AUCDBP-low, AUCDBP-cum, AUCMAP-hi, AUCMAP-low, AUCMAP-cum). All intraoperative pressure data will be collected with either invasive arterial catheterization [Q30 secs] or non-invasive blood pressure monitoring [Q3 min] as determined by the attending anesthesiologist caring for the subject.
- Area under the curve of intraoperative progressive categorical pulse oximetry (SpO2) desaturations (AUCSpO2) including the following:
  - AUCSpO2 < 95% regardless of intraoperative FiO2 values ○
  - AUCSpO2 < 90% regardless of intraoperative FiO2 values ○
  - AUCSpO2 < 85% regardless of intraoperative FiO2 values ○

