#### 7.4.1.2 Postoperative:

- ❶ Area under the curve of  $rSO_2$  desaturations ( $AUC_{rSO_2}$ ) of progressive categorical degrees that will include the following:
  - < 5% of established room air baseline and oxygen supplemented baseline ○ < 10% of established room air baseline and oxygen supplemented baseline ○ < 15% of established room air baseline and oxygen supplemented baseline ○ < 20% of established room air baseline and oxygen supplemented baseline ○ < 25% of established room air baseline and oxygen supplemented baseline ○ < 30% of established room air baseline and oxygen supplemented baseline

baseline ○ < 35% of established room air baseline and oxygen

supplemented baseline ○ < 40% of established room air

baseline and oxygen supplemented baseline ○ < 60% of

absolute measured value (if baseline > 60%) ○ < 55% of

absolute measured value (if baseline > 55%) ○ < 50% of

absolute measured value (if baseline > 50%) ○ < 45% of

absolute measured value (if baseline > 45%) ○ < 40% of

absolute measured value ○ < 35% of absolute measured value

○ < 30% of absolute measured value

○ < 25% of absolute measured value ○ < 20% of absolute

measured value

● Area under the curve for cumulative, high and low postoperative values outside of preestablished, individualized patient blood pressure goals based upon preoperatively observed blood pressure values as well as values clinically accepted to provide adequate organ perfusion. This analysis will be performed for systolic, diastolic and mean arterial pressures (AUCSBP-hi, AUCSBP-low, AUCSBP-cum, AUCDBP-hi, AUCDBP-low, AUCDBP-cum, AUCMAP-hi, AUCMAP-low, AUCMAP-cum). All postoperative blood pressure data will be collected with either invasive arterial catheterization [Q30 secs] or non-invasive blood pressure monitoring [Q15 min] as determined by the attending anesthesiologist caring for the subject in the PACU.

● Area under the curve of postoperative progressive categorical pulse oximetry (SpO2) desaturations (AUCSpO2) including the following:

○ AUCSpO2 < 95% regardless of intraoperative FiO2 values ○

AUCSpO2 < 90% regardless of intraoperative FiO2 values ○

AUCSpO2 < 85% regardless of intraoperative FiO2 values ○

AUCSpO2 < 80% regardless of intraoperative FiO2 values ○

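### Forward stepwise search over 50 nested rSO2 AUCs, read at p < 0.05, is not a 5% test; the false-positive rate is inflated several-fold per outcome

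*Combined protocol and SAP*

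**What the plan says.** Section 15 is the whole statistical plan. For the link between oximetry and outcome it says "Stepwise, forward, multivariable logistic regression analysis will be performed to assess for relationships between cerebral desaturations and any of the measured clinical variables". The criterion attached to this regression reads "with a p value < 0.05 being considered significant". The section gives no candidate list, no handling of collinearity, no multiplicity control and no internal validation.

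Sections 7.4.1.1 and 7.4.1.2 list the rSO2 AUCs. The first entry is "< 5% of established room air baseline and oxygen supplemented baseline". The list runs in 5-point steps to 40%, then through absolute values from 60% down to 20%, and is given once for the intraoperative and once for the postoperative phase. Section 6.3 extends the relative grid to 50%.

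Section 6.4, under exploratory objectives, uses logistic regression to find the most relevant "desaturation value(s) associated with any detrimental clinical outcome(s) monitored in this study". Section 7.4.1 gives the same relationship a different status: "The relationship between the observed cerebral oximetry data and a number of predefined intraoperative and postoperative clinical variables will serve as the primary endpoints".

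**The concern.** Forward selection tries every candidate and keeps the strongest. The p value printed for the winner is computed as if it had been the only variable considered. With dozens of candidates and no correction, that p value falls below 0.05 far more often than 5% of the time when nothing is going on, and the odds ratio beside it is biased away from 1.

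What is at stake is how the pilot's association results are read. A reported harmful rSO2 threshold, labelled significant, could be a product of the search. The comparison of randomised arms by the Wilcoxon test is a separate analysis and is not affected by this point.

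**Working it through.** The plan gives no error-rate or sample-size calculation, so there is no figure of its own to reproduce.

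**Candidates**
- Relative cut-offs (7.4.1.1): 5% to 40% in steps of 5 = 8; two baselines: 8 x 2 = 16.
- Absolute cut-offs: 60% to 20% in steps of 5 = 9.
- Per phase 16 + 9 = 25; two phases (7.4.1.1 and 7.4.1.2): 50.
- With the 5-50% grid of section 6.3 and the same 9 absolute values: (10 x 2 + 9) x 2 = 58.

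**Information available.** With 100 subjects (section 7.1) and assumed event rates of 10%, 25% and 50%, events per candidate are 10/50 = 0.2, 25/50 = 0.5 and 50/50 = 1.0.

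**Upper reference.** If the 50 tests were independent, P(at least one p < 0.05) = 1 - 0.95^50 = 92.3%. They are not independent, so this is a ceiling only.

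**Allowing for collinearity.** Forward selection admits something only if at least one candidate is significant at the first step. That probability was simulated for n = 100 with an outcome unrelated to every AUC. The main entry test was the score test, entering if n r^2 > 3.84. Harmful means a significant candidate whose larger AUC goes with more events.

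| Assumed structure, one null outcome | Any entry | Harmful entry |
|---|---|---|
| One prespecified AUC (nominal) | 5% | 2.5% |
| 50 equicorrelated variables, r = 0.5 | 62% | 31% |
| r = 0.7 | 42% | 21% |
| r = 0.9 | 21% | 10% |
| Simulated rSO2 traces, event rates 10-50% | 23-52% | 11-38% |
| Separate simulation | 28-44% | 14-39% |
| Traces, 25% events, likelihood-ratio entry | 50-53% | 22-28% |
| Traces, 25% events, Wald entry | 23-33% | 15-16% |
| Traces, 25% events, 58 candidates or both hemispheres | 31-49% | 23-33% |

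In rounded terms, the trace results are 25-50% for any entry and 10-40% for harmful entry. The 50 AUCs thus act like about ln(0.75)/ln(0.95) = 5.6 to ln(0.50)/ln(0.95) = 13.5 independent tests. Harmful entry is 11/2.5 = 4 to 38/2.5 = 15 times nominal.

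**Several outcomes.** Section 6.4 covers any detrimental outcome. Section 7.4.1.2 alone lists at least ten that can be scored yes/no: atrial fibrillation, myocardial ischaemia, stroke or TIA, transfusion, nursing-facility admission, readmission, delirium, renal replacement, infection and the composite. With moderate traces, mixed event rates of 5-40% and outcome correlation of 0 to 0.3, the chance of at least one false harmful threshold was:

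| Null outcomes searched | 2 | 3 | 5 | 10 | 15 |
|---|---|---|---|---|---|
| Probability | 39-42% | 52-57% | 67-73% | 84-92% | 92-98% |

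These runs had a per-outcome rate of 21-26%. At the low end of the range (10%), and with independent outcomes, 1 - 0.9^6 = 47% and 1 - 0.9^7 = 52%, so seven outcomes would be needed to pass one half. At 40%, 1 - 0.6^2 = 64%, so two suffice.

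**The case against.** The strongest reply is that this is a 100-subject pilot and section 6.4 labels the search exploratory. Section 6.2 and the synopsis (Criteria for Evaluation) place the primary aim in the comparison of arms. Screening many cut-offs to generate hypotheses is legitimate in that setting. This stands in part. It would excuse unadjusted p values shown as descriptive, but section 15 declares them significant. Section 7.4.1 calls the same relationship the primary endpoints. That conflict does not settle that the search is confirmatory. It means the two sections must be reconciled.

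Four stronger readings are tempting, and the documents do not support them.

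- *A search over 50 AUCs usually finds a harmful threshold for a single outcome.* The 92% figure needs independent tests and counts both directions. With nested cut-offs the harmful rate stayed below one half in every trace scenario.
- *The search covers 80 AUCs.* Adding 9 x 2 = 18 blood pressure and 6 x 2 = 12 SpO2 AUCs would raise the rate further. Section 6.4, however, lists blood pressure as its own regression and names no logistic search over SpO2, and no section describes a pooled search.
- *The selected cut-off will be built into the multicentre trial.* Section 6.2 carries forward outcome variables that differ by arm, and the Study Rationale in section 5 carries forward endpoints and design. Use of an rSO2 threshold is at most an inference.
- *The chosen cut-off is close to arbitrary.* Collinearity makes unstable selection plausible, but selection stability was not calculated here.

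**Conclusion.** The point holds as a several-fold inflation of false positives. Followed as written, the p value of a selected rSO2 AUC is not a 5% test. For one outcome and no true association, roughly 25-50% of trials would show some AUC at p < 0.05, and roughly 10-40% one in the harmful direction. Across three or more outcomes a false harmful threshold is more likely than not under the moderate trace assumptions; at the lowest per-outcome rate it takes about seven.

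The count of 50 and the absence of any correction come from the documents. The percentages rest on assumed event rates and trace correlations, so only their order of magnitude should be relied on. Two readings of the plan are inferred: that 0.05 is the entry rule as well as the significance level, and that the AUC is the predictor. Section 15 does not say which side of the model desaturation is on; section 6.4 implies the predictor side. Counting harmful entries at the first step slightly overstates what a final model would report.

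**What to change.** Do not read stepwise p values against 0.05. Either of two replacements would do.

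1. **Keep the search and price it.** For each rSO2 AUC and each outcome searched, compute an arm-adjusted score statistic, and take the maximum over all of them. Permute subjects' outcome records, all outcomes together, within randomised arm, and recompute the maximum each time. The p value is (1 + number of permuted maxima at or above the observed one) / (number of permutations + 1). Repeat the whole selection in bootstrap samples, and report how often each cut-off is chosen together with optimism-corrected odds ratios. This keeps the aim of section 6.4.
2. **Name one rSO2 AUC in advance.** For each sufficiently frequent outcome, fit one logistic model with that AUC, randomised arm and one or two preoperative covariates such as age, and show the other cut-offs descriptively. That is 3 to 4 terms: with 25 events, 25/4 = 6.3 to 25/3 = 8.3 events per term; with 15 events, only 3.8 to 5. This option gives up the threshold search.

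Under either option, state the candidate list, the outcomes and the direction of the model, and keep rare outcomes such as stroke descriptive. Do not adjust for single-lung time: it arises after randomisation and desaturation may change it, since section 7.4.1.1 records surgery being paused to re-inflate the lung. Reconcile sections 6.4 and 7.4.1 on whether this analysis is exploratory or primary.

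The cost is plan wording and some programming, with no new data collection. Fewer associations will be called significant.
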